6.3 Strategies for Recruitment and Retention

Practice recruitment. Network dentists of all specialties, hygienists, and dental therapists in the Midwest and Northeast regional nodes will be approached for interest in study participation by node coordinators. The National Coordinating Center (NCC) will maintain the practitioner database to facilitate recruitment and track Network practitioner training. The node coordinators will use several methods to recruit practices including network webinars, network newsletters, announcements at network meetings, email blasts, and directly targeting practitioners with existing relationships with node coordinators. Interested practitioners will be made “research ready” by being oriented to the Network and completing any institutionally required human subjects research protection training.

Patient participants will be recruited directly by practitioners within each practice during a routine dental visit. Practices will aim to recruit at least 2 patients per month. Practitioners or practice staff will approach consecutive adult patients with a chart documented smoking history and invite them to participate. To increase interest in the FreSH study, practitioners will be given posters and flyers for their offices. Interested patients will begin a self-screening process. The screening process will take place on a tablet computer. Patients will read a study description and indicate whether they are interested in the study. If they are interested, they will complete an eligibility screen on the tablet.

Retention of Practices and Providers within Practices. Several steps will be taken to retain practices. (1) Procedures for recruitment and retention have been tailored to dental practices through an iterative development process involving the piloting of study procedures and feedback from practices. Practitioners will be given a “quick guide” detailing all recruitment procedures. (2) The NCs will leverage their existing relationships with PBRN practitioners to keep them engaged. They will be in regular contact with the practices, providing feedback and support. (3) Incentives will be provided to each practice including “lunch and learns” and study monogrammed trinkets designed to increase commitment to the study. (4) Practitioners will be remunerated \$100 per patient participant who receives the study intervention and a tablet computer to obtain electronic informed consent (when not using a paper consent form) and administer baseline surveys that they may keep at the end of the study if allowable by their affiliated institution.

Retention of Patients. As part of the enrollment process, patient participants will provide contact information, including mobile/home/work phone numbers, email address, mailing address, and contact information for up to five alternative contacts. They will be asked to provide only phone numbers/addresses at which they give permission for the study team to contact them and leave messages (phone call/voicemails, text messages, and email). Participants will be asked to rank their preferred methods of communication

and Hennepin Healthcare study staff will try their preferred method first. Follow-up assessments will be conducted via online survey (using REDCap). Patient participants will be emailed and/or texted a direct link to the follow-up survey on the first date of their follow-up window. Participants will be able to complete their follow-up surveys on a web browser on any Internet-connected device including a smartphone or tablet. Those who do not respond within 24 hours will be sent the survey link every 24 hours for up to 5 days. If the participant does not complete the follow-up survey by the 5th day, Hennepin Healthcare study staff will begin contacting the participant by telephone and offer the option of doing the follow-up survey via telephone interview. Study staff will attempt to reach participants for up to two weeks. If we do not reach them by phone, email or text, Hennepin Healthcare study staff will call their alternate contacts for updated contact information and send a final letter to their mailing address stating that we have been unable to reach them including a contact information sheet, and a postage paid envelope. We may also send a paper version of the survey. Participants may choose to complete the survey out of the two-week timeframe without prompting from study staff. In addition, their dental practitioner will be contacted by the node coordinator and asked for any updated contact information and to reach out to the participant to ask them to contact the study. Study staff will maintain numbers screened, eligible, consented, randomized, and completed assessments. Whenever possible, we will attempt to collect reasons for dropping out of the study.

Patient participants will receive a custom printed bag with the study name and logo. The bag will contain study materials, information on smoking and oral health, a flyer for the state quitline and some small tokens of appreciation such as stylus pens that have the study name, phone number, and email address printed on them so that they also serve as reminders of study participation (total value of study promotional items will be < \$10). Throughout their participation, participants will be treated with respect and study staff will aim to maintain excellent rapport. Study staff will frequently express appreciation to participants and emphasize that by participating they are making a valuable contribution to science. Finally, patient participants will be remunerated for their time and efforts to encourage retention during the follow-up period. Patient participants will receive \$20 for the after-visit survey and \$20 for completing each of 3 follow-up surveys. Patients in the NRTS arm who report abstinence will be sent a Bedfont iCOquit expired breath CO monitor intended for single patient use and will receive an additional \$50 for using the iCOquit to take an exhaled breath CO test. Participants will keep the CO monitor (a \$68 value) as it is for single user only. Finally, 10-12 patient participants will be paid \$50 for completion of an end of study interview.

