4 OBJECTIVES AND OUTCOME MEASURES

4.1 Primary

Objective	Brief Description/Justification of Outcome Measure	Outcome Measured By	Time Frame

Assess the effectiveness of NRTS compared to ET on 6-month biologically verified 7-day point prevalence abstinence from combusted tobacco
	
Seven day point prevalence abstinence (no combustible tobacco use in the past 7 days) is the recommended outcome for cessation induction trials as it measures a clinically-significant change in the long term, but reflects that participants may quit at any time following the intervention.⁴¹ Biochemical verification with breath carbon monoxide adds additional rigor to the primary outcome.⁴² Carbon monoxide will detect combustible tobacco use and not nicotine replacement therapy use.
	
Self-report survey using timeline follow-back and iCO quit personal CO monitor.
 
Following the CO test and result, we will compute a binary variable: abstinent vs. non-abstinent. Those who report abstinence on all 7 days prior to the 6-month follow-up and have a CO test result of <6ppm will be considered abstinent. Those who report smoking in the past 7 days, or have a CO result >6ppm, or who do not respond to the survey will be classified as non-abstinent.
	
6 months following baseline

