5 STUDY DESIGN

Study design. This is a 2-arm, phase 2, cluster randomized effectiveness clinical trial that will be conducted in the National Dental PBRN, which is a network of participating dental practitioners who conduct practice-based oral health research. This study will utilize the resources of the ARC and NCC. The node coordinators will utilize ARC's established communication methods to inform prospective dental practitioners about the study opportunity. Enrolled practitioners will recruit and enroll patients during routine dental care appointments.

Study Population: The practitioner study population will include National Dental PBRN practitioners, dental therapists and hygienists. We will enroll approximately 50 practices across the Midwest and Northeast Regions of the PBRN. Each practice will recruit approximately 24 patients for a patient population of 1200.

Means of Data Collection: Data collection will be centralized. Survey data will be collected using the REDCap platform administered by the NCC. CO data will be collected via the iCO quit personal CO monitor. The iCO quit devices will be mailed to participants who will take the test using an app downloaded to their smartphone. Interviews will be completed by phone and audiorecorded.

Interview. Following a practitioner's participation in the trial, we will conduct stakeholder interviews with 10-12 dentists, 10-12 other staff, and 10-12 patients. Topics include patient and practitioner experiences with the intervention, provider perceptions of barriers and facilitators to adoption and tools/supports/structures needed for implementation.

Collection Timeframe: Following screening and consent, patient data will be collected at 5 timepoints, baseline, immediately following the baseline visit, and target of 1 month, 3 months, and 6 months following the visit. For practitioners, data collection will occur prior to initiation of site data collection and following completion of site data collection.

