8.3 Follow up Visits¹

Data collection timepoint 2, Day 0 (allowable range 0-14)

- Following visit, administer after visit survey via email, text, or phone.

Data collection timepoint 3, Day 30 (allowable range 28-44)

- Administer 1-month follow-up survey via email, text or phone.
 - Assess adverse events via survey.

Data collection timepoint 4, Day 90 (allowable range 83-104)

- Administer 3-month follow-up survey via email, text or phone.
 - Assess adverse events via survey.

Data collection timepoint 6, Day 180 (allowable range 173-210)

- Administer 6-month follow-up survey via email, text or phone.
 - Assess adverse events via survey.

Data collection timepoint 7, Day 180 (allowable range 174-234)

- Participants who are abstinent will take a CO test

Data collection timepoint 8, Day 180 (allowable range 173-240)

¹ Note: Participants may choose to complete the survey out of the timeframe without prompting from study staff.

- 10-12 patient participants in NRTS condition complete an interview about acceptability of NRTS and attitudes about future implementation of NRTS

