9.1.6 CO test (target day: within one week of 6-month follow up survey)

Participants who report being abstinent for the past 7 days on the 6-month follow-up survey will be sent, via overnight mail, a portable CO monitor (iCOquit, Bedfont Scientific) with instructions for use. Participants will be instructed to take the CO test within 24 hours of receipt. If they do not take the test within 24 hours, the study will provide email, text, or phone reminders daily for 14 days. Patient participants will download the iCOquit app onto their cellphones. The study will provide a username and password for the app. The participant will then follow the instructions on the app to take a CO test. Hennepin Healthcare study staff will log into the app (with the pre-specified username and password given to the participant) to get the test result. Thus, all the data from the iCOquit is deidentified (a username and passcode provided by the study, and the participant's test result). They will be instructed to delete the app once CO data is received. Participants will be paid \$50 for a completed CO test.

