12.1 Study Hypotheses

Hypothesis 1 (primary): Participants receiving the NRTS intervention will have a higher frequency of biochemically confirmed abstinence at 6 months post enrollment compared to ET.

Hypothesis 2a: Participants receiving NRTS will be more likely to have a 24-hour quit attempt than ET.

Hypothesis 2b: Participants receiving NRTS will have greater reductions in smoking heaviness compared to baseline than ET.

Hypothesis 3a: Use of nicotine replacement therapy (patch and lozenge) will mediate the effect of NRTS on biochemically confirmed abstinence at 6 months post enrollment.

Hypothesis 3b: Perceptions of NRT safety and efficacy will mediate the effect of NRTS on biochemically confirmed abstinence at 6 months post enrollment.

Hypothesis 3c: Intention to use NRT will mediate the effect of NRTS on biochemically confirmed abstinence at 6 months post enrollment.

Hypothesis 3d: Intention to quit smoking will mediate the effect of NRTS on biochemically confirmed abstinence at 6 months post enrollment.

Hypothesis 4a: NRTS will be considered feasible to administer in dental settings.

Hypothesis 4b: NRTS will be acceptable to practitioners and patients.

Hypothesis 5: NRTS will be cost effective.

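### Section 6.3 gives the CO monitor and the $50 test payment to the NRTS arm only, contradicting sections 5, 8.3 and 9.1.6, Appendix A, and a primary endpoint that needs a CO result in both arms

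*Protocol*

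**What the plan says.** **Who gets the test.** Protocol section 6.3, in its paragraph on patient remuneration: "Patients in the NRTS arm who report abstinence will be sent a Bedfont iCOquit expired breath CO monitor intended for single patient use". That sentence goes on to an additional $50 "for using the iCOquit to take an exhaled breath CO test". The next sentence lets participants keep the monitor, valued at $68.

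The other places that describe the CO test name no arm:

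- Section 5, on data collection: "The iCO quit devices will be mailed to participants who will take the test using an app downloaded to their smartphone".
- Section 8.3, the follow-up schedule: "Participants who are abstinent will take a CO test".
- Section 9.1.6, the CO procedure: "Participants who report being abstinent for the past 7 days on the 6-month follow-up survey will be sent, via overnight mail". It adds daily reminders for 14 days and pays $50 "for a completed CO test".
- Appendix A, the patient schedule of events, lists the CO test for patients in general.

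**What the endpoint needs.** Under section 4.1, those who report abstinence on all 7 days and "have a CO test result of <6ppm will be considered abstinent". The primary hypothesis in section 12.1 compares the arms on this verified outcome: "Participants receiving the NRTS intervention will have a higher frequency of biochemically confirmed abstinence at 6 months post enrollment compared to ET".

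**The concern.** Whether a self-reported quitter can become a primary-endpoint success depends on receiving the device and using it. Section 6.3 is an explicit operational rule that supplies both the device and the incentive in one arm only.

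It cannot be passed over as obviously unintended. The protocol restricts other activities to NRTS on purpose: patient interviews (8.3, 9.1.7), staff surveys (9.1.8, 9.1.9) and staff interviews (9.1.10). Someone setting up payments from section 6.3 could take the CO restriction as one more of these.

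At stake is equal measurement of the primary outcome. A CO test missed within its window (days 174 to 234 in section 8.3) cannot be obtained later.

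**Working it through.** **1. The passages side by side**

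| Place | Monitor or test for | $50 for |
|---|---|---|
| 6.3 | NRTS patients reporting abstinence | the same NRTS patients |
| 5 | participants | not stated |
| 8.3 | abstinent participants | not stated |
| 9.1.6 | participants reporting 7-day abstinence | participants completing the test |
| Appendix A | patients, no arm named | not stated |

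Section 8.3 is informative. In the same list it limits the interview to NRTS in so many words and does not limit the CO test. So four places are arm-neutral and one is not.

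**2. What section 4.1 does with an untested quitter**

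The abstinent category needs a CO value. The non-abstinent list covers reported smoking, CO above 6 ppm and survey non-response. A patient who reports abstinence but has no CO result is not named. Such a patient cannot be counted as abstinent under the definition as it stands, and nothing else in 4.1 limits the effect of a missing test.

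**3. The plan's own power figure**

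Inputs from section 12.2: 50 clusters of 24 (600 per arm), ICC 0.013, ET rate 5.5%, difference 5.0 points, two-sided 5%.

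- Design effect: 1 + 23 × 0.013 = 1.299. Effective n per arm: 600 / 1.299 = 461.9.
- Standard error: √[(0.055 × 0.945 + 0.105 × 0.895) / 461.9] = 0.01778.
- Power: Φ(0.05 / 0.01778 − 1.96) = 80.3%.

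This equals the entry in Table 11.1, and the same formula matches all 45 cells. The calculation assumes the same outcome definition in both arms, as 9.1.6 provides, so reconciling the text changes neither N nor power.

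**4. Size of the bias if section 6.3 were followed**

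Suppose the true verified rate p is the same in both arms, so NRTS has no effect. Let f be CO-test completion among ET quitters relative to NRTS quitters, with untested patients not counted as abstinent. The spurious difference is p × (1 − f). The documents give no value for f, so it is shown as a range, with p at the ends of the planning range in 12.2.

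| f | p = 4.5% | p = 5.5% |
|---|---|---|
| 1 (as in 9.1.6) | 0 | 0 |
| 0.75 | 1.1 points | 1.4 points |
| 0.5 | 2.25 points | 2.75 points |
| 0 (no ET monitors, 6.3 taken literally) | 4.5 points | 5.5 points |

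The intermediate rows stand for partial adherence, for example sending monitors to both arms but paying only NRTS. The last row is as large as the 5.0-point effect the trial is designed to detect.

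**5. How a test would react in the extreme row**

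With ET at 0, NRTS at 5.5% and effective n of 461.9, a pooled two-proportion test has:

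- null standard error √(2 × 0.0275 × 0.9725 / 461.9) = 0.01076;
- alternative standard error √(0.055 × 0.945 / 461.9) = 0.01061;
- rejection in favour of NRTS with probability Φ[(0.055 − 1.96 × 0.01076) / 0.01061] = 99.9%.

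At 4.5% the figure is 99.6%. The nominal value is 2.5%. This is an approximation, not the planned analysis.

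**The case against.** The strongest reply is that section 6.3 is one stray sentence in recruitment and retention text. The operative procedure (9.1.6), the schedule (8.3, Appendix A) and the design section (5) are all arm-neutral. This stands. A reader might infer from 6.3 that the control arm cannot reach the primary endpoint; that is not true of the protocol as a whole.

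Second, dental practices have no described role in CO testing. Data collection is centralised, the monitor is mailed, and central study staff retrieve the result (9.1.6) and enter it (16.2). This also stands: the risk lies with one central team. That team would notice an arm with no monitors sent, since section 16.4.1 schedules weekly data review. Unequal payment would be less conspicuous.

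Third, the 99% figures do not come from the planned model. Section 12.3 specifies mixed-effects logistic regression. With no ET events, the treatment coefficient suffers complete separation. In an ordinary logistic check of 0/600 against 33/600, the Wald p-value is about 0.999, while the likelihood-ratio chi-square is about 47. A near-certain false positive is therefore not established; it would depend on a test type that the protocol does not state.

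Two further inferences fail. One is that ET would be judged on self-report and NRTS on CO, costing power. No section accepts self-report alone for ET at 6 months. The other is that no analysis could recover the comparison. Self-reported 6-month smoking is collected by the same survey in both arms, so an equally ascertained unverified comparison would remain, although it is not the primary endpoint.

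None of this removes the contradiction on who receives the device and the money.

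**Conclusion.** The point holds as an internal contradiction that bears on the primary endpoint and needs correcting. It does not show that the protocol chose arm-specific verification; the weight of the text points the other way.

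The harm is conditional on the central team acting on section 6.3. If it did, ET successes would be under-counted and the bias would favour NRTS. The size runs from zero, with equal completion, to 4.5 to 5.5 points when no ET quitter is tested. Those figures assume equal true verified rates within the planning range and untested patients not counted as abstinent. The intermediate completion values are illustrative.

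**What to change.** In section 6.3, replace the opening of the sentence on the iCOquit monitor so that it applies to *participants in either arm who report 7-day abstinence on the 6-month survey*. State that monitor, payment and reminders are identical by arm, as in 9.1.6. Check that the consent text and the follow-up SOP say the same. Report, by arm, the number who reported abstinence, the number sent a monitor and the number who completed the CO test.

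The cost is a one-sentence amendment and a document check. Taking 5.5% as the verified ET rate and 85% verification (12.2), about 600 × 0.055 / 0.85 = 39 ET patients would report abstinence. At $68 for the monitor plus $50, that is about 39 × $118 = $4,602 before postage. Section 9.1.6 already commits the trial to this.

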6.4 Treatment Assignment Procedures

This is a group randomized trial. All patients within a practice are assigned to the same condition. Practices will be instructed not to tell their patients to which condition the practice has been assigned until after the baseline survey is completed to prevent selection bias.

6.4.1 Randomization Procedures

The NCC Data Manager, who will have no contact with participants or practices, will conduct randomization. Practices will be randomized to NRT or ET (approximately 25 practitioners per condition). Condition assignment will be stratified by practice level patient demographic data (highest percentage minority race/ethnicity vs. lowest) and practice payer mix (highest vs. lowest public insurance/free care). We will use block randomization with permuted block size of 2 and 4. Randomization will occur once the practice has completed all activities required for onboarding.

6.5 Participant Withdrawal or Discontinuation from Study Procedures/Intervention

6.5.1 Reasons for Participant Withdrawal or Discontinuation from Study Procedures/Intervention

Participants are free to withdraw from participation in the study at any time upon request.

Participants may choose to discontinue the intervention or study procedure but continue to be followed.

Study sites could be closed by the PI if there are persistent problems with recruitment, or if study recruitment goals are met prior to the site completing recruitment.

6.5.2 Handling of Participant Withdrawals from Study or Participant Discontinuation of Study Intervention

Reasons for participant withdrawal will be documented on a dedicated Case Report Form.

Patient participants will be instructed by study staff to discontinue use of the patch and/or lozenge entirely if a severe reaction develops. They will be instructed to contact the study team (not their dentist) as soon as possible if they experience a SAE or if they have a reaction for which OTC labeling suggests seeing a provider. Practitioners will receive training on how to manage adverse events of NRT. However, for this study,

patient participants and practitioners will be advised that the study staff, not the practitioner, is responsible for managing study-related AEs. Patients who have a study-related SAE (as determined by the study PI and the IRB) will be advised to discontinue use of the study treatment (NRT or ET). All study related SAEs will be followed to resolution using a Case Report Form.

Power calculations and sample size estimates for this study account for 11% lost to follow-up/withdrawal. Thus, we will not replace subjects who withdraw unless attrition and withdrawal exceeds 11% of our planned study sample.

